3. PATIENT SELECTION

Eligible patients will have with metastatic castration-resistance prostate cancer who have experienced disease progression after treatment with Enza. . Prior treatment with Enza pre or post-chemotherapy is required. Prior treatment with docetaxel is allowed but not required. Patients will have been treated with continuous ADT. Patients will continue on ADT with LHRH agonist (i.e. Zoladex, Trelstar, Eligard or Lupron) or LHRH antagonist (Degarelix) if not surgically castrated throughout the duration of the study to inhibit endogenous testosterone production. Patients will be treated in a single-arm study sequentially with Dex then Enza. A total of 13 patients will be recruited across 2 treatment sites in the initial phase of the trial, after which an additional 7 patients will be recruited if initial benchmarks for non-futility are met.

3.1 Eligibility Criteria

- 3.1.1 Patients must have histologically or cytologically confirmed adenocarcinoma of the prostate
- 3.1.2 Patients must have metastatic disease radiographically documented by CT/MRI or bone scan; measurable disease is not necessary for inclusion.
- 3.1.3 Age ≥ 18 years.
- 3.1.4 ECOG performance status ≤ 2 (Karnofsky $\geq 60\%$, see Appendix A).
- 3.1.5 Life expectancy of greater than 3 months in the opinion of the investigator
- 3.1.6 Patients must have acceptable organ and marrow function as defined below:
 - absolute neutrophil count $\geq 1,500/\text{mcL}$
 - platelets $\geq 100,000/\text{mcL}$
 - hemoglobin ≥ 8 ; transfusion is allowed
 - total bilirubin $\leq 1.5 \times$ institutional upper limit of normal
 - AST(SGOT)/ALT(SGPT) $\leq 2.5 \times$ institutional upper limit of normal
 - Creatinine clearance ≥ 30 by Cockcroft-Gault formula
- 3.1.7 Patients must have progression after prior treatment with Enza at any point in the disease course (pre- or post-chemotherapy).
- 3.1.8 Prior treatment with docetaxel is allowed but not required.
- 3.1.9 Prior treatment with other second line hormone therapy is allowed (e.g. flutamide, bicalutamide, nilutamide, ketoconazole, abiraterone, ARN-509). Patients must be off these therapies for at least 4 weeks prior to starting treatment.
- 3.1.10 Prior treatment with Xofigo ($^{223}\text{Radium}$), Provenge, mitoxantrone and cabazitaxel is allowed.
- 3.1.11 Patients must have rising PSA on two successive measurements, at least 2 weeks apart.
- 3.1.12 Patient must be treated with continuous androgen ablative therapy (e.g. goserelin, leuprolide, triptorelin, or degarelix, if he has not had prior surgical castration) and have castrate levels of testosterone ($< 50 \text{ ng/dL}$ or 1.7 nmol/L).
- 3.1.13 Ability to understand and the willingness to sign a written informed consent document.

3.2 Exclusion Criteria

- 3.2.1 Patients who have had chemotherapy or radiotherapy within 4 weeks prior to entering the study or those who have not recovered from adverse events due to agents administered more than 4 weeks earlier (persistent toxicity \geq Grade 1) .
- 3.2.2 Patients who have received any other investigational agents within the last 4 weeks.
- 3.2.3 History of allergic reactions attributed to compounds of similar chemical or biologic composition to Dex or Enza.
- 3.2.4 Any use of systemic corticosteroids in the prior 4 weeks.
- 3.2.5 Uncontrolled diabetes mellitus
- 3.2.6 History of seizure, underlying brain injury with loss of consciousness, transient ischemic attack within the past 12 months, cerebral vascular accident, brain metastases, and brain arteriovenous malformations.
- 3.2.7 Patients receiving any medications or substances that are inhibitors or inducers of CYP2C8 are ineligible (e.g. gemfibrozil, rifampin, trimethoprim, pioglitazone). Because the lists of these agents are constantly changing, it is important to regularly consult a frequently-updated list such as <http://medicine.iupui.edu/clinpharm/ddis/>; medical reference texts such as the Physicians' Desk Reference may also provide this information. As part of the enrollment/informed consent procedures, the patient will be counseled on the risk of interactions with other agents, and what to do if new medications need to be prescribed or if the patient is considering a new over-the-counter medicine or herbal product.
- 3.2.8 Uncontrolled intercurrent illness including, but not limited to, ongoing or active infection, symptomatic congestive heart failure, unstable angina pectoris, cardiac arrhythmia, or psychiatric illness/social situations or geographical condition that would limit compliance with study requirements.

3.3 Inclusion of Women and Minorities

This study is focused on prostate cancer, therefore is applicable to men only. Women and children will not be included on this study. Men from all ethnic and race groups are eligible for this study.

4. PATIENT REGISTRATION AND ENROLLMENT PLAN

4.1 Registration Procedures

- 4.1.1 All patients must sign a written informed consent form before study specific screening procedures are performed. Screening procedures to evaluate patient eligibility for the study will be conducted within 28 days prior to Cycle 1 Day 1. If the patient meets eligibility and screening requirements he will initiate on therapy. All required screening, treatment and post-treatment study procedures and assessments must be done within 7 days (+/-) of the specified study visit date.
- 4.1.2 Initial Registration Process: Eligible patients will be registered on study centrally at the Sidney Kimmel Comprehensive Cancer Center by the Lead Site Study Coordinator.

To register a patient, the following documents must be completed and emailed to the Lead Center Program Coordinator at Johns Hopkins, [name], at [contact]:

- Signed/dated patient consent form
- Eligibility checklist
- Copies of the prostate cancer pathology report
- Copies of pre hormone therapy/chemotherapy or radiation therapy
- Screening labs
- CT and bone scan reports
- Other materials may also be sent if considered pertinent for confirming patient eligibility

The Lead Center (Johns Hopkins) will review the documents to confirm eligibility. To complete the registration process the Lead Center will:

- Assign a patient study number
- Patients found to be ineligible for participation after being consented will be considered screen failures, and documented as such in the Screening and Enrollment Log
- Once eligibility is confirmed, all patients must commence treatment within 7 calendar days.

4.2 General Guidelines

Following registration, patients should begin protocol treatment within 7 days. Issues that would cause treatment delays should be discussed with the Principal Investigator. If a patient does not receive protocol therapy following registration, the patient's registration on the study may be canceled. The Study Coordinator should be notified of cancellations as soon as possible.

5. TREATMENT PLAN

5.1 Study Design

Patients with metastatic castration-resistant prostate cancer who are treated with continuous androgen-deprivation therapy and have progressed after prior treatment with Enza will be treated on a single-arm, open-label, multi-site study to determine the response rate of Enza after treatment with Dex. Prior treatment with docetaxel is allowed but not required. Secondary objectives will be radiographic response rates to Enza for patients with measurable disease, response rates to Dex, progression-free survival (PSA and radiographic) for treatment with Dex, AR-V7 positivity with correlation to response to Dex and Enza, and any change in AR-V7 positivity occurs as a result of treatment with Dex.

5.2 Study Treatments and Scheme

Treatment will be administered on an outpatient basis. No investigational or commercial agents or therapies other than those described below may be administered with the intent to treat the patient's malignancy.

5.2.1 Study Treatments

[figure not shown]
Patients will continue on ADT with LHRH agonist (i.e. Zoladex, Trelstar, Eligard or Lupron) or LHRH antagonist (Degarelix) if not surgically castrated throughout the duration of the study.

Patients will be prescribed Dex 2mg tablets to take once daily orally with food for 28 days/cycle continuously. Patients who have PSA progression after one cycle will continue on Dex for a second cycle. Patients with continued increase in PSA (if satisfies progression based upon PCWG2 definition) will begin Enza. Patients with declining PSA after 2 cycles of Dex will continue on Dex until PSA progression. Every 3 cycles patients will have repeat bone/CT scans to evaluate treatment response. Patients will remain on treatment with Dex until evidence of PSA progression (per the PCWG2 definition) or disease progression on CT scan (per RECIST criteria), or progressive bone metastatic disease (per the PCWG2 definition).

At time of progression, Dex will be stopped via a rapid taper over one week if patients were treated for >30 days. Patients will be instructed to take 1 mg Dex for 7days, then stop. However, ongoing use of corticosteroids will be allowed if indicated for bone pain or adrenal suppression.

Patients will then be prescribed Enza 40 mg tablets and instructed to take 4 tablets per day orally with or without food for 28 days/cycle continuously. Dose adjustments and delays will be allowed as per standard of care with treatment with Enza. Patients will have PSA checked monthly. All patients will remain on Enza for 3 cycles regardless of PSA response. At the end of 3 cycles of Enza all patients will come off study. Those patients with PSA or radiographic progression will come off study and be offered standard of care or another clinical trial. Those patients with PSA or radiographic response after 3 cycles will be offered to remain on Enza as standard of care therapy.

5.2.2 Treatment Scheme

5.3 Duration of Follow Up

Patients will be followed for 4 weeks after removal from study or until death, whichever occurs first. Patients removed from study for unacceptable adverse event(s) will be followed until resolution or stabilization of the adverse event.

5.4 Criteria for Removal from Study

A patient may be removed from the study for a variety of reasons, including:

1. As defined by the protocol, evidence of disease progression based on radiographic progression or worsening symptoms while on Enza.
2. Unacceptable adverse events
3. Intercurrent illness that prevents further participation
4. Experiencing a treatment delay of longer than 2 weeks due to drug toxicity attributed to Dex. Patients who experience treatment delay while on Enza will remain on study as per protocol.
5. Patient refuses further treatment through the study and/or withdraws consent to participate
6. Need for “stress dose” glucocorticoids due to a life threatening medical condition.
7. Patients is noncompliant with respect to taking drugs, keeping appointments, or having tests required for the evaluation of drug safety and efficacy
8. General or specific changes in the patient's condition that render the patient unacceptable for further treatment in this study in the judgment of the investigator
9. Under no circumstance will care of a withdrawn patient be adversely affected by a decision to withdraw or be withdrawn from the study.
10. Ongoing response after 12 cycles of dexamethasone.

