SKCCC Protocol #: J1548

ClinicalTrials.gov Identifier: NCT02491411

TITLE: A Pilot Study of Dexamethasone Therapy Prior to Rechallenge with Enzalutamide in Men with Metastatic Castration-Resistant Prostate Cancer

Dex EXTends Enza Response (The DEXTER Trial)

Organization:

Johns Hopkins

Lead Site Principal Investigator:

[name].
The Sidney Kimmel Comprehensive Cancer
[name]
[name]
[contact]
[contact]
[contact]

Co-Investigator:

[name].

Statistician: [name]

Lead Study Coordinator:

[name]

Research Study Coordinator/Data Manager

[name]

[name]

[contact] Office

[contact] Fax

[contact]

Responsible Research Nurse: [name]

Coordinating Center:

The Sidney Kimmel Comprehensive Cancer Center at Johns Hopkins

[name].

[name]

[name]

[contact]

Email: [contact]

Participating Site: The Akron General Medical Center, Akron, OH

Version # / Version Date: #1.0, Date 4/10/15

Version # / Version Date: #2.0, Date 09/17/2015

Version # / Version Date: #3.0, Date 08/24/2016

SYNOPSIS

Title: A Pilot Study of Dexamethasone Therapy Prior to Rechallenge with Enzalutamide in Men with Metastatic Castration-Resistant Prostate Cancer

Phase of Study: Pilot

Objectives: To determine if treatment with dexamethasone (Dex) followed by enzalutamide (Enza) provides PSA and objective response, in patients who have previously had disease progression after Enza. Prior treatment with docetaxel is allowed but not required.

Study Design: The study is a single arm, open-label study wherein patients with metastatic castrate resistant prostate cancer (mCRPC) will be treated with Dex 2mg PO daily until PSA progression, then treated with Enza 160mg PO daily.

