1. OBJECTIVES

1.1 Primary Objectives

- 1.1.1 To determine the PSA response rate to Enza after treatment with Dex (Dex) therapy. Responses will be determined by PSA criteria as defined by Prostate Cancer Working Group (PCWG2) criteria. The baseline will be defined as the initiation of Enza. The percentage of patients with >50% PSA response will be the primary endpoint.

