2.4 Study Hypothesis

The hypothesis of the study is that Dex-mediated down-regulation of the glucocorticoid receptor could reverse one resistance mechanism to Enza therapy and allow for renewed therapeutic sensitivity to Enza.

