12.2 Sample Size/Accrual Rate

The treatment regimen would be considered of insufficient activity for further study in these population if PSA response rate is 5% or less, and the minimum required level of efficacy that would warrant further study with the proposed regimen is a 25% PSA response rate. The sample size is calculated to detect an improved PSA response rate from 5% to 25%. A minimax Simon two-stage design is planned. A total of 13 patients will be entered in the first stage. If none of them show PSA response after Enza, the treatment regimen will be terminated and we will conclude the regimen is ineffective. If ≥ 1 subjects has PSA response, then additional 7 patients will be studied. If a total of 2 or fewer subjects achieve PSA response in stage one and two combined, we consider this regimen ineffective. If a total of 3 or more respond, we conclude the regimen is promising and warrant further study. The trial could be terminated early also as soon as 3 PSA responses with the post-Dex Enza treatment are confirmed.

The maximum sample size will be 20. Patients who receive at least one dose of Dex will be evaluable for the primary endpoint of PSA response. Those who do not start Enza subsequent to Dex will be considered as non-responders in the analysis. This design provides 90% power to reject a 5% PSA response in favor of 25% response rate, with a type I error of 0.1. The chance of early stopping is 0.51 when the response rate is less than 5%.

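### Does scoring patients who leave the study still responding to Dex as Enza non-responders spoil the primary PSA response rate?

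*Protocol*

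**What the plan says.** The synopsis describes men who "will be treated with Dex 2mg PO daily until PSA progression, then treated with Enza 160mg PO daily", and section 5.2.1 says that "Patients with declining PSA after 2 cycles of Dex will continue on Dex until PSA progression". Section 5.4, item 10, adds a ground on which a patient may leave the study: "Ongoing response after 12 cycles of dexamethasone". Twelve cycles of 28 days are 336 days, or 48 weeks.

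Section 12.2 sets the primary denominator: "Patients who receive at least one dose of Dex will be evaluable for the primary endpoint of PSA response". It also settles the case in question: "Those who do not start Enza subsequent to Dex will be considered as non-responders in the analysis". The SAP repeats both sentences.

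The primary objective in section 1.1 is "To determine the PSA response rate to Enza after treatment with Dex (Dex) therapy", and section 2.4 hopes that Dex will "allow for renewed therapeutic sensitivity to Enza". PSA response is measured from the value at Enza start (sections 1.1, 12.1 and 12.3). Section 12.3 and the SAP plan one overall PSA response rate with a 95% confidence interval and response to Dex and Enza by AR-V7 status at entry. They also plan objective response in measurable disease, Kaplan-Meier summaries of progression on Dex, and quality-of-life summaries. None of the PSA rates is limited to men who start Enza, and no table of reasons for not starting is specified.

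**The concern.** A man still responding to Dex after 48 weeks has had about the best outcome the first phase can give. If he is removed at that point he has no Enza baseline PSA, yet he counts exactly like a man whose rechallenge failed, including toward the stage 1 rule that stops the trial if none of 13 respond.

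The primary objective and the hypothesis speak of response to Enza. The all-Dex rate equals the rate among starters multiplied by the share who start, so everyone who never starts dilutes it, whatever the reason. A low result could mean that Dex does not restore sensitivity to Enza, or that part of the sample was never rechallenged. The overall rate alone does not say which, and a starters' rate chosen after the data are seen would lack the protection of pre-specification.

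**Working it through.** **Inputs.** From section 12.2 and the SAP: null rate 5%, target rate 25%, 13 patients in stage 1 with a stop at 0 responders, 7 more in stage 2, success at 3 or more of 20. The number removed under item 10, k, is not given. Table 1 in section 2.2.1 gives PSA response rates to Dex but no durations. I assume k = 0, 1 or 2 of 20.

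**The plan's own figures.** With X₁ responders in stage 1, P(success) = P(X₁ ≥ 3) + P(X₁ = 2)·P(Bin(7, p) ≥ 1) + P(X₁ = 1)·P(Bin(7, p) ≥ 2).

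- p = 0.25: 0.6674 + 0.2059 × 0.8665 + 0.1030 × 0.5551 = 0.903 (stated 90%).
- p = 0.05: 0.0245 + 0.1109 × 0.3017 + 0.3512 × 0.0444 = 0.074 (within the stated 0.1).
- Early stopping at 5%: 0.95¹³ = 0.513 (stated 0.51).

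The design is correct when 5% and 25% refer to all Dex-treated patients, which is the denominator that section 12.2 sets.

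**Effect of k certain non-responders, the others responding at 25% (at 5% for the type I error).**

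| k | Expected rate if all 20 enrol, 25% × (20 − k)/20 | P(0 of 13), all k in stage 1, 0.75^(13 − k) | Type I error |
|---|---|---|---|
| 0 | 25.0% | 0.024 | 0.074 |
| 1 | 23.75% | 0.032 | 0.065 |
| 2 | 22.5% | 0.042 | 0.056 to 0.058 |

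The ranges reflect whether the patients fall in stage 1 or stage 2. The false-positive risk falls, and the chance of a wrong stop at stage 1 rises by at most 0.042 − 0.024 = 0.018.

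**What a starters' rate would add.** Every responder has started Enza, so the numerator is unchanged. Exact (Clopper-Pearson) 95% intervals:

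| Responders | All Dex-treated (20) | 19 starters | 18 starters |
|---|---|---|---|
| 3 | 15.0% (3.2 to 37.9) | 15.8% (3.4 to 39.6) | 16.7% (3.6 to 41.4) |
| 5 | 25.0% (8.7 to 49.1) | 26.3% (9.1 to 51.2) | 27.8% (9.7 to 53.5) |

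The largest shift is 27.8 − 25.0 = 2.8 points, against an interval for 5/20 that is 49.1 − 8.7 = 40.4 points wide. The decision rule counts responders, so an added starters' rate could not alter the decision.

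**Fit with the objectives.** The synopsis and section 12.1 ask whether Dex followed by Enza gives responses, and section 12.2 judges the regimen. An all-Dex denominator answers that directly. Section 1.1 can be read either way, and section 12.2 fixes the reading.

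**The case for a change.** The best case for a change goes beyond item 10. Men may also fail to start Enza because of toxicity, withdrawal or death, so the share of non-starters could exceed one or two in 20. If 25% is taken as the rate among starters, the planned rule has power 0.880 with 5% non-starters, 0.854 with 10% and 0.786 with 20% (all three shares are assumptions). The synopsis gives the all-Dex denominator but leaves out the sentence on scoring non-starters. One supplementary rate and a short disposition table would cost almost nothing and would fix the second denominator in advance.

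Part of this stands: neither the starters' rate nor a count of non-starters by reason is pre-specified. The power figures, however, show what happens under a target that section 12.2 does not set. For 25% over all Dex-treated patients the power is 0.903.

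Nor would the information be lost. The Kaplan-Meier summary should show men removed at 48 weeks without progression as censored, blood for AR-V7 is drawn at Enza start under section 6.2.2, and quality of life is summarised at each visit on Enza. Any competent report of a 20-patient trial states how many began the second drug and why the others did not.

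The supplementary rate would also be weak evidence. It is conditional on an event after treatment begins and leaves out both the longest Dex responders and the early drop-outs. Appendix C, writing of RECIST response, bars subset analyses that exclude patients from supporting efficacy conclusions.

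**Conclusion.** No change to the plan is needed. Scoring non-starters as non-responders is a deliberate, conservative definition, stated in the same words in section 12.2 and the SAP. It fits the regimen question, does not raise the type I error, and leaves the stated 90% power correct for the population to which it applies. Followed as written, it leads to a sound conclusion.

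Under the assumption of one or two item-10 removals in 20, the starters' rate would differ from the planned rate by 0.8 to 1.7 points at 3 responders and by 1.3 to 2.8 points at 5. With no such removals, item 10 has no effect. Removal is worded as permitted rather than required, and the documents give no frequency.

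The missing starters' rate is a reporting detail that analysts can supply from the counts as a descriptive figure, with no bearing on the decision. Section 5.2.1 on continuing Dex and item 10 of section 5.4 can be read together, as a treatment rule and a ground for leaving the study. No view is taken here on the clinical rule itself.

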5.5 Concomitant Therapy

The use of any concurrent medication from screening and while on study, prescription or over-the-counter, is to be recorded on the patient's CRF along with the reason the medication was taken. In addition, tobacco and alcohol use will be collected. Concurrent use of another clinical investigational drug or device while on study is prohibited. Supportive care medications are

permitted with their use following institutional guidelines. For patients who did not undergo orchiectomy, concurrent treatment with LHRH analogue is mandatory and must be recorded.

The following supportive care medications are considered permissible during the study.

- Conventional multivitamins, selenium and soy supplements
- Dutasteride or finasteride if being used to treat BPH and only if patients are on the medication for at least 3 months prior to Study Day 1
- Bisphosphonate and denosumab usage is allowed only if patients are on the medication for at least 3 months prior to Study Day 1
- Transfusions and hematopoietic growth factors per institutional practice guidelines

5.6 Prohibited Concomitant Medications

Concomitant therapy during the treatment phase of the study with any of the following listed is prohibited:

- Chemotherapy
- Immunotherapy
- Bicalutamide, nilutamide, flutamide
- Systemic ketoconazole (or other azole drugs such as fluconazole and itraconazole)
- Abiraterone acetate
- Prednisone or other glucocorticoids, except if indicated for bone pain or adrenal suppression at the time of tapering of dexamethasone
- Diethylstilbestrol, PC-SPEs, and other preparations such as saw palmetto thought to have endocrine effects on prostate cancer
- Radiopharmaceuticals such as Xofigo (²²³Ra), strontium (⁸⁹Sr) or samarium (¹⁵³Sm)
- Other experimental drugs or treatments

